## 9.4.4. Physical Activity Level Data

### 9.4.4.1. Lower Extremity Activity Scale (LEAS)

The Lower Extremity Activity Scale score will be a integer value from 1 (bed bound) to 18 (competitive athlete). The number and percentage of subjects whose activity score is improved (increased), worsened (decreased) or have no change will be shown by treatment group for Weeks 4, 8, 16, 24, 56 and 80 (using LOCF for any missing data). The change from baseline to each post-baseline visit (using LOCF for missing data), and for the worst

change from Baseline (over all post-Baseline visits) will be summarized, and analyzed using Cochran-Mantel-Haenszel test.

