6.3.4. Activity Level Monitoring Endpoints

The Lower Extremity Activity Scale (LEAS) is an 18-point integer scale reflecting the subjects physical function status, ranging from 1 (bed bound) to 18 (competitive athlete).

The accelerometry endpoints of average daily minutes of physical activity, average daily physical activity counts, minutes of moderate to vigorous physical activity (MVPA), minutes of bouts MVPA, and average daily step count will be calculated from the raw data.

The Activity Level Monitoring endpoints are listed below:

- *Lower Extremity Activity Scale: change from Baseline to Weeks 4, 8, 16, 24, 56 and Week 80 (all subjects).*
- *Change from Baseline to Weeks 16 and 56 in average daily minutes of physical activity (a subset of subjects).*
- *Change from Baseline to Weeks 16 and 56 in average daily physical activity counts (a subset of subjects).*
- *Change from Baseline to Weeks 16 and 56 in average daily minutes of moderate to vigorous physical activity (a subset of subjects).*
- *Change from Baseline to Weeks 16 and 56 in average daily minutes of bouts (sustained) moderate to vigorous physical activity (a subset of subjects).*
- *Change from Baseline to Weeks 16 and 56 in average daily step count (a subset of subjects).*

09001776e193181b056ApprovedApproved On: 08-10-2019 08:56 (GMT)

A valid day of monitoring will be defined as 10 or more wear hours in a 24-hour period as verified from accelerometer output. During Screening, a complete monitoring period will be defined as containing at least 1 valid weekend day of data and a minimum of 4 valid days of monitoring. During activity level monitoring between Week 14 and the Week 16 visit and between Week 54 and the Week 56 visit, a complete monitoring period will be defined as containing at least 2 valid weekend days of data and a minimum of 8 valid days of monitoring.

For the purposes of the MVPA endpoints, the three intensity levels of activity are defined as light (100 – <1,500 counts), moderate (1,500 – <6,500 counts), and vigorous (≥6,500 counts). The data will be further summarized as total daily time (minutes) for each intensity level.

A “bout” of moderate to vigorous activity is defined as 10 or more consecutive minutes above the moderate physical activity level threshold, with allowance for interruptions of 1 or 2 minutes below the threshold.

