6.4. Covariates

For all models analyzing the continuous primary and secondary efficacy endpoints (except rescue medication) the corresponding Baseline value will be used as a covariate, in addition to Baseline diary average pain. Study site will be fitted as a random effect in the ANCOVA models. The randomization stratification variables of index joint (hip or knee), NSAID cohort (celecoxib, naproxen and diclofenac), and highest Kellgren-Lawrence grade of any Hip/Knee joints (grade 2, 3 or 4) will be included as fixed effects.

A listing of subjects with mis-matches between the stratification variables entered at randomization and the case report form data (including central lab data for Kellgren-Lawrence grade) will be provided. In analysis models, the strata entered at randomization will be used, but for descriptive summarization of the population and identification of subgroups, the strata as indicated on the case report form data will be used.

For the models analyzing the amount and number of days of rescue medication use the model will include terms for Baseline WOMAC Pain, Baseline diary average pain and stratification factors.

The analysis of the incidence of treatment discontinuation due to lack of efficacy will include model terms for baseline WOMAC Pain subscale score, Baseline Diary Average Pain, index joint, Kellgren-Lawrence grade, NSAID group and treatment group.

0900177 (e-s) 1811656 Approved Approved On: 03-10-2019 08:56 (GMT)

For treatment response endpoints relating to WOMAC Pain and PGA, the Baseline WOMAC Pain and PGA values will be used respectively as covariates in the analysis model, in addition to the stratification parameters of index joint, highest Kellgren-Lawrence grade of any hip or knee joint, NSAID group and Baseline diary average pain. For the OMERACT response value, the Baseline WOMAC Pain subscale score will be used to represent the Baseline score covariate, in addition to the covariates named above (Baseline diary average pain, and the three stratification factors).

Additional analyses of the three co-primary endpoints will examine the treatment interactions with Study site and Country. Note, separate analyses will be performed for the individual NSAID groups.

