One hundred imputed samples will be used in this analysis. In order to pre-define the analysis (and not to allow the results to change if run again), the following seeds will be used in the creation of the multiple imputed data: WOMAC scores [1] 7001-7100; and [2] 8001-8100; PGA scores: [3] 9001-9100 and [4] 10001-10100; and diary pain scores: [5] 11001-11100 and [6] 12001-12100. Imputed data for the PGA will be rounded to integer scores in the range 1 to 5. Imputed data for the WOMAC subscale and Average scores, and for the diary pain scores <0 and >10 will be truncated to 0 and 10, respectively. Imputed data for the WOMAC items of Pain when Going Up or Down Stairs and Pain when Walking on a Flat Surface will be rounded to integer scores in the range 0 to 10. The ANCOVA analysis described in [Section 8.1.1](#) (with covariates in [Section 6.4](#)) will be used for each imputation dataset, and the overall results will be calculated to take account of the variability both within and between imputation datasets using standard methods (Little & Rubin, 2002), which are described in [Appendix 3.2](#).

0900177ed1931781b0561ApprovedApproved On: 08-10-2019 08:56 (GMT)

This analysis will be used for the co-primary efficacy endpoints at Week 16, plus secondary analyses at other time points, and also for a range of secondary efficacy endpoints at all time points up to Week 56. When using the multiple imputation method described above for time points earlier than Week 56, then the reason for missing data is assessed up to the end of the window for that particular time point (see [Appendix 1.1](#)).

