The change from Baseline in the Lower Extremity Activity Scale to Weeks 4, 8, 16, 24, 56 and 80 and worst post-Baseline score will be analyzed using CMH test and stratified by the combined levels of the three stratification factors (Section 6.4). LOCF will be used for imputation of missing data. The change from Baseline to all weeks (including Week 80) will be summarized showing the number and percentage of subjects with any worsening score (change<0), no change, or improvement (change>0), as well as each category of change, and mean (with standard deviation) and median change.

The CMH test will be stratified by the combinations of the three stratification factors (Section 6.4). For any analysis using the CMH test, if there are too few subjects in any stratification combination group (defined as <15 subjects in any stratification factor) then an unstratified test will be performed.

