8.2.1. Primary Analysis (Efficacy)

The primary analysis for the co-primary endpoints will use ANCOVA with covariates of Baseline score, Baseline diary average pain, Index Joint (Knee or Hip), Highest KL grade (2, 3 or 4), NSAID cohort, Treatment Group, and study site as a random variable. The primary analysis set is the ITT analysis set. The primary analysis will use multiple imputation as described in [Section 7](#), and analysis using the ANCOVA model, with combination of results from imputation analyses using standard methods as described in [Section 8.1.1](#). These three primary endpoint analyses (two for Japan) will be used to assess the primary objective of the study.

Primary Endpoint Sensitivity Analyses

A number of sensitivity analyses will be performed on the primary efficacy endpoints in order to assess the robustness of the conclusions for the primary objective. These relate to the analyses for missing data and the analysis population, the homogeneity of the results across factors that may influence efficacy, and for a secondary analysis of the PGA. The analyses described below will not be subject to the testing strategy described for multiple comparisons of the primary analyses (given in [Section 4.2](#)). As such, assessment of all treatment comparisons will be made independent of results over the co-primary endpoints or the two treatment comparisons for each analysis.

The ITT analysis set is used in the analyses numbered 2 to 5 below, and the PP analysis set is used in analysis number 1 below.

1. Per-Protocol Analysis Set.

The primary analysis described above will be repeated, but using the Per-Protocol analysis set (as described in [Section 5.2](#) and [Section 5.6](#)) in place of the ITT analysis set. This analysis will assess the robustness of the efficacy conclusions to subjects who have more strictly adhered to protocol inclusion and exclusion criteria, and to protocol defined study procedures.

2. Alternative Missing Data Analyses.

There are three additional analyses that will assess the robustness of the efficacy conclusions to the choice of multiple imputation as the primary method for accounting for missing data. These analyses are described in detail in [Section 7](#).

In the first and second analyses, the primary ANCOVA analysis model described in [Section 8.1.1](#) will be repeated, but using BOCF and LOCF respectively for missing data (note these are single imputation analyses).

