Change from Baseline in LEAS to Weeks 4, 8, 16, 24, and 56, and worst post-baseline score.	ITT	CMH test	Treatment group [1]	LOCF (weeks 4, 8, 16, 24, and 56) and worst score	Secondary Endpoint Analysis
Change from Baseline in Accelerometry endpoints (daily minutes of physical activity, MVPA and bouts MVPA; daily step count; daily physical activity counts) to Weeks 16 and 56	Accelerometry analysis set	negative binomial	BL Score, BL Diary Average Pain, Index Joint (Knee/Hip), Highest KL grade (2, 3 or 4), NSAID cohort, Treatment Group	Observed	Secondary Endpoint Analysis
Change from Baseline in Accelerometry endpoints (daily minutes of physical activity, MVPA and bouts MVPA; daily step count; daily physical activity counts) to Week 56	Accelerometry analysis set	negative binomial	BL Score, BL Diary Average Pain, Index Joint (Knee/Hip), Highest KL grade (2, 3 or 4), NSAID cohort, Treatment Group	LOCF	Secondary Endpoint Analysis
Incidence of primary composite adjudication joint safety endpoint	ITT	Poisson model for risk difference (exposure-adjusted)	Exposure, exposure*treatment	Observed	Primary Joint Safety Analyses
Incidence of primary composite adjudication joint safety endpoint	ITT	Poisson model for risk ratio (exposure-adjusted)	Treatment group, offset by log-exposure	Observed	Secondary Joint Safety Analyses
Incidence of primary composite adjudication joint safety endpoint	ITT	Exact analyses for risk difference and ratio (percentage)	Treatment group	Observed	Secondary Joint Safety Analyses
Incidence of secondary composite endpoint, individual adjudication joint safety endpoints (RPOA-1, RPOA-2, RPOA-1/2, SIF, Primary ON, Pathological fracture), TJR, and TJR and any adjudication outcome	ITT	Poisson model for risk difference (exposure-adjusted)	Exposure, exposure*treatment	Observed	Secondary Joint Safety Analyses
Incidence of secondary composite endpoint, individual adjudication joint safety endpoints (RPOA-1, RPOA-2, RPOA-1/2, SIF, Primary ON, Pathological fracture), TJR, and TJR and any adjudication outcome	ITT	Poisson model for risk ratio (exposure-adjusted)	Treatment group, offset by log-exposure	Observed	Secondary Joint Safety Analyses

090017764931816561Approved/Approved On: 08-10-2019 08:56 (GMT)

09/01/2019 17:56:56 Approved On: 08/10/2019 08:56 (GMT)

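### LEAS change is tested by a stratified CMH test with no Baseline LEAS term, no treatment difference and no confidence interval, although the SAP adjusts coarser scales for their own Baseline

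*SAP*

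**What the plan says.** SAP section 6.3.4 describes the measure: "The Lower Extremity Activity Scale (LEAS) is an 18-point integer scale". It is completed by all subjects at Baseline and at Weeks 4, 8, 16, 24, 56 and 80.

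SAP section 8.1.2 places LEAS under categorical data: change from Baseline and "worst post-Baseline score will be analyzed using CMH test and stratified by the combined levels of the three stratification factors", with LOCF for missing data. The table in SAP section 8.2.5 has a row for "Change from Baseline in LEAS to Weeks 4, 8, 16, 24, and 56, and worst post-baseline score". Its method is the CMH test and its only model term is treatment group. The footnote to that table makes the test unstratified if any of the 18 combined strata holds fewer than 15 subjects. Protocol section 9.4.4.1 names the same test: LEAS change "will be summarized, and analyzed using Cochran-Mantel-Haenszel test".

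The planned LEAS output (SAP sections 8.1.2 and 8.2.2, item 11) is counts improved, worsened and unchanged, each level of change, and mean, SD and median by arm.

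Other scales are handled differently:
- **General rule, SAP section 6.4:** "For all models analyzing the continuous primary and secondary efficacy endpoints (except rescue medication) the corresponding Baseline value will be used as a covariate".
- **PGA, five levels:** SAP section 7 states "Imputed data for the PGA will be rounded to integer scores in the range 1 to 5", and SAP section 8.2.1 states "The primary analysis for the co-primary endpoints will use ANCOVA with covariates of Baseline score, Baseline diary average pain". The CMH test for PGA is only a sensitivity analysis.
- **Single WOMAC pain items, integers 0 to 10:** ANCOVA with their own Baseline (SAP section 8.2.2, item 2).
- **Accelerometry, about 360 subjects:** negative binomial models with their own Baseline (SAP section 8.2.2, item 12).

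**The concern.** A change score that is not adjusted for Baseline carries the full Baseline variability into the comparison. When follow-up regresses on Baseline with a within-arm slope other than 1, a model with Baseline as covariate estimates the same treatment difference with smaller variance in large samples. The Baseline LEAS value is already collected, so leaving it out gives up precision for nothing.

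The number of levels does not explain the choice, because PGA and the WOMAC items are coarser and are adjusted.

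The second gap does not depend on any correlation. A stated secondary objective is to characterize changes in physical activity level. For LEAS the plan gives a p-value and raw summaries by arm, but no estimated difference between arms and no interval around it.

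**Working it through.** **Inputs.** Neither document gives an SD, effect size or Baseline to follow-up correlation for LEAS. The nearest activity figures are for actigraphy, in Protocol section 9.1: SD 20, correlation 0.75, SD of change taken as 14, 120 subjects per arm, differences of 5 and 6 minutes, stated power 79% and 91%. They are used here only as an indication.

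**Reproducing the stated figure.**
- SD of change = 20 × √(2 × (1 − 0.75)) = 14.14, which the protocol rounds to 14.
- Power = Φ(δ / (SD × √(2/n)) − 1.96). With SD 14 and n = 120, the standard error is 14 × √(2/120) = 1.807.
- δ = 5: Φ(2.766 − 1.96) = 79.0%. δ = 6: Φ(3.320 − 1.96) = 91.3%. Both agree with the protocol.

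**Same inputs with Baseline as covariate.**
- Residual SD = 20 × √(1 − 0.75²) = 13.23, so the standard error is 1.708.
- Power becomes 83.3% and 94.0%.

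**General formula at a landmark week.** With equal SD s at both times, the change score has variance 2s²(1 − r) and the adjusted score s²(1 − r²). The ratio is (1 + r)/2, so the information lost is (1 − r)/2.

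| r | Variance ratio | Information lost | Interval width saved, 1 − √ratio |
|---|---|---|---|
| 0.4 | 0.70 | 30% | 16.3% |
| 0.6 | 0.80 | 20% | 10.6% |
| 0.75 | 0.875 | 12.5% | 6.5% |
| 0.8 | 0.90 | 10% | 5.1% |

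**Does stratification recover the loss?** A simulation compared the stratified mean-score CMH test with ANCOVA on Baseline and strata. It used an 18-level integer score, 1000 per arm and 18 strata, with assumed SD 3, mean 9 and stratum shares, and 1500 replicates per r. The information lost was 31% at r = 0.4, 21% at 0.6, 14% at 0.75 and 12% at 0.8. Stratifying by index joint, NSAID cohort and KL grade does not stand in for Baseline LEAS under these assumptions.

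**Sensitivity to the SD ratio.** Let k be the follow-up SD divided by the Baseline SD. The loss is (1 − kr)² / (1 + k² − 2kr).
- k = 1.2, r = 0.75: 0.10² / 0.64 = 1.6%. For r from 0.4 to 0.8 the loss runs from 18% down to 0.3%.
- k = 0.8, r = 0.75: 0.40² / 0.44 = 36.4%. For r from 0.4 to 0.8 it runs from 46% down to 36%.

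The loss vanishes only when kr = 1, that is, when the slope of follow-up on Baseline is 1.

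**Limits.** The variance comparison assumes the mean-score form of CMH. SAP section 8.1.2 names that form for the Neuropathy Impairment Score but names no form for LEAS. The formula applies to change at a fixed visit. It does not apply to the worst post-Baseline score, whose correlation with Baseline cannot be derived from the documents.

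**The case against.** The strongest defence is that LEAS is an ordered list of descriptors whose steps are not evenly spaced. Levels 10 to 12 grade how active a job is, 13 to 15 the frequency of relaxed exercise, and 16 to 18 the frequency of vigorous sport. The SAP places LEAS beside the Neuropathy Impairment Score under categorical data and also uses CMH for the mPRTI items, so there is a recognisable pattern. This is a fair reason to keep the CMH test. It is not a reason to omit the adjusted analysis, because the SAP accepts ANCOVA for a five-level ordinal co-primary.

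Several stronger readings are tempting, and the documents do not support them:
- **That the test is wholly unadjusted.** It is stratified by the three randomization factors. Only Baseline LEAS is missing, unless the rule for fewer than 15 subjects removes the strata.
- **That 10% to 30% is an established loss.** It is a variance figure that rests on an assumed r and equal SDs. The protocol's one activity correlation points to the low end, and LOCF may raise the correlation and shrink the loss.
- **That the trial needs more subjects.** The planned 1000 per arm is justified in Protocol section 9.1 by joint safety and the co-primary endpoints, not by LEAS.
- **That the SAP breaches its own covariate rule.** The rule covers continuous efficacy endpoints. LEAS is listed as an activity-monitoring endpoint, although its analysis sits among the secondary efficacy analyses.
- **That LEAS is the only activity-related measure in all subjects.** WPAI activity impairment is also scheduled for everyone, and is analysed by Baseline-adjusted ANCOVA.

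**Conclusion.** The point holds as a modest efficiency and reporting gap. The LEAS analysis leaves out a Baseline value that is already collected and gives no treatment difference or interval, while the SAP adjusts coarser scales and the other activity endpoints for their own Baseline. At landmark weeks, with equal SDs and a mean-score CMH test, the loss is about 12.5% of information (about 6.5% in interval width) at r = 0.75. It is 10% to 30% of information (5% to 16% in width) over an assumed r of 0.8 to 0.4. An unequal SD ratio can take it close to zero or well above 30%.

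A reader might infer that the planned test is invalid. It is not: type I error is unaffected, and LEAS lies outside the multiplicity-controlled testing strategy. The missing interval estimate needs none of these assumptions and is the firmer half of the point.

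**What to change.** Add an analysis of LEAS change at Weeks 4, 8, 16, 24 and 56 with the SAP's existing ANCOVA: Baseline LEAS, Baseline diary average pain, the three stratification factors, treatment, and study site as a random effect. Report the LS mean difference from NSAID with its 95% CI. State the missing-data rule; retaining the planned LOCF would leave the model as the only change. Keep the stratified CMH test as supportive and for the worst score, and name its form.

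In the same edit, reconcile Week 80. SAP section 8.1.2 lists it among the weeks tested, SAP section 8.2.2 (item 11) says it is summarized only, and the table in section 8.2.5 stops at Week 56. Those three places also word the rule for fewer than 15 subjects differently (per factor, per stratum level, per combined level), so one wording should be chosen.

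The cost is SAP text and reuse of an existing program, with no new data. Protocol section 9 lets the SAP modify planned analyses and asks for an amendment only for major changes to the primary endpoint or its analysis, so none is needed here.

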8.1.3. Analyses for Binary Endpoints

Binary response parameters, and the incidence of rescue medication use and treatment discontinuation due to lack of efficacy will be analyzed using logistic regression for binary data, with covariates described in Section 6.4. Output will show the number and percentage of subjects in each response category, and odds ratios (with 95% CIs) for the treatment comparisons shown in Section 4.1.

Separate analyses of the joint safety endpoints will use exposure time as the denominator (giving results in terms of events per 1000 patient years of exposure) and then number of subjects as the denominator (giving results in terms of percentages). Both these analyses will be performed for risk difference and risk ratio. The analyses using number of subjects as the denominator will analyze risk difference and ratio between both tanezumab groups and NSAID using exact methods. The analyses using exposure as the denominator will analyze risks using Poisson models. The model for risk difference will have a linear link, poisson errors, and model terms for exposure and exposure-by-treatment (where treatment is 1 for tanezumab group and 0 for NSAID). The model for risk ratio will have a log-link, poisson errors, and model term for treatment group with log-exposure as the offset variable.

Results will show event rates by treatment group, and difference/ratio of tanezumab doses versus NSAID, all shown with 95% confidence intervals, and significance tests for the treatment comparisons.

Events will be included in summaries if they occur up to the end of the safety follow-up period or 26 weeks (planned duration of the follow-up period + 2 weeks) after the end of the treatment period, whichever is later.

For the joint safety event analyses, the observation period is defined as the time from first SC dose to study completion or discontinuation for subjects who did not have an event, or time from first SC dose to the earliest event for subjects who did have at least one event.

0900177ed193181b656Approved\Approved On: 08-10-2019 08:56 (GMT)

